#### 9.1.1.3. Study Design for GBS etiology: Exploratory data mining-based signal detection

[figure not shown]
The study design and research approach for this objective was taken largely from Maro et al., with adaptations. This signal detection analysis will use tree-based scan statistics to broadly search for vaccines, drugs, and infections that may be potential risk factors for GBS.

The method was originally designed and used to detect the association between a specific product (drug or vaccine) and a broad, unspecified range of health outcomes organized in a hierarchical "tree" structure based on their diagnosis codes. For a medical product of interest—influenza vaccine, for example—vaccinees' diagnoses recorded during *post-vaccination* follow-up time are scanned to look for statistically unusual clustering of diagnoses. This method has been used for drugs as well as vaccines.

In this project's application of the method, the analysis will be anchored on the outcome of interest (i.e., GBS) and the software will scan for statistically significant clusters of exposures (i.e., infection diagnoses, vaccines, and drugs) in a pre-specified number of days (e.g., 84) *prior* to the occurrence of the outcome. The hierarchical organization of exposures enables detection of, not only product-specific effects, but also class- or type-wide effects (e.g., mRNA vaccines).

A case-crossover design, which minimizes bias by automatically adjusting for time-invariant confounding, will be implemented (see Figure 1). First, incident cases of GBS will be identified using the ICD-10-CM diagnosis code based algorithm, as described in the below Table 1. Incident exposures (i.e., infection diagnoses, vaccines, and drugs) in the exposure assessment window (to be defined in the SAP) preceding each GBS case will then be identified. Exposures and GBS will not be permitted on the same day because of the inability to distinguish the sequence of events within the same day in administrative claims data. The time-to-event from the exposure to the GBS diagnosis date will be identified. The analysis assesses when a greater than expected frequency of precipitating events occurs that puts the GBS outcome in the risk window. Log-likelihood ratios and Monte Carlo hypothesis testing are used to scan the tree for a potential signal. Further details on this data mining technique are in Section 9.1.7.3.

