Figure 1. Example design diagram for the self-controlled case crossover design for GBS.

#### 9.1.2. Setting for Research Question 1

GBS will be identified, for all objectives in this protocol, using an algorithm based on Goud and colleagues (2021), which is very similar to other algorithms.  GBS will be defined as incident primary GBS diagnosis (G61.0) in the inpatient setting, or incident GBS in any setting and any position, with a hospitalization within 7 days where GBS is the primary diagnosis. Incidence is defined using 365-day washout for G61.0 or G65.0 in any care setting.

Table 1. Algorithm for incident GBS

ICD-10-CM code	Setting of code	Definition of "incident"	Performance
G61.0 (Guillain- Barré syndrome)	1) G61.0 as primary hospital discharge diagnosis or 2) G61.0 in any position, any setting, followed by a hospitalization within the 7 subsequent days	No evidence of GBS (G61.0 [GBS] or G65.0 [Sequelae of GBS], any setting, any position) in the 365 days	PPV from study using Medicare data: 79%

for which G61.0 was the primary hospital discharge diagnosis.	prior to the first diagnosis code of interest.	(95% CI, 64% - 94%) 
The date of GBS onset will be considered the date of the first eligible G61.0 code in any setting.		

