# 9.1.3.3. Variables for GBS etiology: Exploratory data mining-based signal detection

# 9.1.3.3.1. Exposure for GBS etiology: Exploratory data mining-based signal detection

One exposure tree will be developed with top-level categories of vaccines, drugs, and infections. This tree, with hierarchal branches, will allow for the detection of potential associations with GBS on both a specific and group level.

Individuals will be permitted to have multiple exposures if the exposure incidence criteria are met. Rules to define an incident exposure will be included in the SAP. If an individual receives multiple exposures within the same branch of the tree on the same day, then only one of those exposures will be included in the analysis. In this situation, the exposure with the smallest count of unique users over the study period will be retained to increase numbers for the rarer exposures.

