#### 9.1.7.3.1. Data mining analyses and statistical methods

TreeScanTM software (www.treescan.org) will be used to analyze data via a self-controlled case-crossover design. In brief, the tree-based scan statistics use log-likelihood ratio tests to detect elevated frequencies of codes in electronic health data that have been grouped into a hierarchical tree structure and automatically adjusts for multiple overlapping scenarios inherent to data mining. The test statistic is computed via Monte Carlo hypothesis testing. Under the alternative hypothesis, there is at least 1 exposure, or group of exposures, for which there is a temporal cluster of GBS cases during some time interval in the observation window.

The important analytic information in the self-controlled case-crossover design using TreeScan is the time from the exposure to the outcome, within the prespecified observation window. The observation window for analysis (e.g., 84 days) is divided into a risk window and a comparison window. Both "fixed risk window" and "varying risk window" approaches are possible. In a fixed risk window analysis using TreeScan, these values are defined *a* 

priori (e.g., days -21 through -1 prior to GBS diagnosis as the risk window; days -84 through -43 as the comparison window). In a varying risk window analysis, the risk window is allowed to move within the overall observation window, while the comparison window varies accordingly and consists of all the days that are not in the risk window being evaluated. Exposure and GBS will not be permitted on the same day (day 0) because of the inability to distinguish the sequence of events within the same day in administrative claims data.

The self-controlled case-crossover design is compatible with the following 4 tree-based scan statistics: conditional and unconditional Bernoulli tree-based scan statistics for fixed risk window analyses, and conditional and unconditional tree-temporal analyses for varying risk window analyses. The specific statistic(s) that will be used will be specified in the final SAP.

Analyses will be performed with a threshold for statistical significance of p = 0.05 (1-sided).

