estimated date that symptoms first appeared per information in the medical record, and this date will be the date used in the final analysis. The GBS onset date is crucial to determining whether the outcome occurred during the risk or control window. Abstractors and adjudicators will be blinded, to the extent possible by redaction, to whether the GBS case occurred in the vaccination risk or control window. Only deidentified data (e.g., relativized dates) will be shared with HPHCI for the analyses. Only aggregate data will be shared externally, including with Pfizer and FDA. Individual-level data will not be shared between RPs or with the study sponsor. Medical records will be obtained from participating RPs in a manner compliant with the Health Insurance Portability and Accountability Act (HIPAA) and local privacy regulations. Hospital charts will be obtained directly through requests from RPs using identifiers obtained from administrative claims data. Designated protected health information users at each RP will link the protected health information with masked patient identification numbers, dates of birth, and provider information for the patients identified for medical chart abstraction.

Notably, medical records will not be 100% obtainable from participating RPs. Section 9.2.7.2. includes a description of how potential events with unobtainable medical records will be handled in the analyses.

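### The data-mining scan takes the first GBS claim as onset and bars only same-day exposures, so drugs and infection codes prompted by early GBS symptoms can signal as risk factors; a prespecified lagged companion scan would expose this.

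*Protocol*

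**What the plan says.** Table 1 in Section 9.1.2, which serves every objective, fixes the outcome date: "The date of GBS onset will be considered the date of the first eligible G61.0 code in any setting". Section 9.1.1.3 builds the scan on that date: "The time-to-event from the exposure to the GBS diagnosis date will be identified". The same section bars exposures on the GBS date itself and gives within-day sequencing in claims as the reason: "Exposures and GBS will not be permitted on the same day because of the inability to distinguish the sequence of events". Section 9.1.7.3.1 repeats the rule and the reason.

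Section 9.1.7.3.1 gives as its example of a fixed design "days -21 through -1 prior to GBS diagnosis as the risk window; days -84 through -43 as the comparison window". It also allows a varying design, in which "the risk window is allowed to move within the overall observation window". The exposures are set in Section 9.1.3.3.1: "One exposure tree will be developed with top-level categories of vaccines, drugs, and infections".

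No lag, induction gap or symptom-onset date is mentioned for this objective. Section 9.1.9.3 lists time-varying confounding (with seasonality as the example), tree organisation, under-capture and the tie-break rule as limitations. It does not mention exposures prompted by the disease itself.

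For the chart-reviewed SCRI, Section 9.2.3.2.2.1 handles dating differently. The adjudicator records the "estimated date that symptoms first appeared per information in the medical record, and this date will be the date used in the final analysis", and the section describes that date as crucial for assigning a case to the risk or control window.

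**The concern.** Symptoms can precede the first G61.0 code, and the protocol's handling of the chart-reviewed SCRI accepts that the two dates may differ. In that gap a patient may be given a drug for the first symptoms, or an infection code may be entered during early work-up. The scan would date such a record before onset, although it followed onset.

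Self-control does not help. It removes confounders that are constant within a person, whereas this bias arises because the days just before the code differ from earlier days in the same person. A varying risk window could settle on exactly those days.

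The objective is to identify vaccines, drugs and infections potentially associated with GBS. A list in which causes cannot be told apart from treatments of early disease serves that purpose poorly and uses follow-up effort on the wrong nodes.

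**Working it through.** The protocol states no power, sample size or onset-to-code interval for this objective, so there is no figure to reproduce. The check asks how little symptom-prompted exposure would be needed for an unrelated drug to signal.

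**Inputs from the protocol**
- Example fixed windows (Section 9.1.7.3.1): risk 21 days, comparison 42 days.
- Significance threshold 0.05, one-sided (Section 9.1.7.3.1).
- Case numbers: about 2,000 (Section 4, Study size); at least 1,000 plus at least 2,000 in preliminary counts (Section 9.1.5). Both refer to the incidence and descriptive objectives, so N = 2,000 and N = 3,000 are used as a range.

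**Assumptions not in the protocol**
- An unrelated exposure occurs in q = 1% or 3% of cases over the 63 days, evenly in time.
- x further cases have the exposure in the risk window because of early symptoms.
- The scan's multiplicity adjustment is imitated by a per-node threshold of 0.05/100 or 0.05/1000.

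**Method.** Under no association, the share of exposures in the risk window is 21/(21+42) = 1/3. With total n = Nq + x and risk-window count r = Nq/3 + x (rounded), find the smallest x for which P(Bin(n, 1/3) ≥ r) falls below the threshold. The apparent rate ratio is (r/21)/((n−r)/42).

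Worked case, N = 2,000, q = 1%: background 20, of which 7 fall in the risk window. With x = 18, n = 38 and r = 25; the exact tail is 4.3e-5, below 5e-5; the rate ratio is (25/21)/(13/42) = 3.85; and 18/2,000 = 0.90% of cases.

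| N | q | x at 0.05 | x at 0.05/100 | x at 0.05/1000 | % of cases at 0.05/1000 | Rate ratio at 0.05/1000 |
|---|---|---|---|---|---|---|
| 2,000 | 1% | 7 | 15 | 18 | 0.90 | 3.85 |
| 2,000 | 3% | 11 | 23 | 28 | 1.40 | 2.40 |
| 3,000 | 1% | 9 | 18 | 22 | 0.73 | 3.20 |
| 3,000 | 3% | 13 | 27 | 33 | 1.10 | 2.10 |

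These are thresholds at the expected counts, not power figures.

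**What a lag would do.** Suppose the gap from a symptom-prompted exposure to the first code is exponential with mean m (assumed). The share with a gap longer than L days is exp(−L/m), an upper figure for what stays in the shifted risk window.

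| Mean gap m (days) | L = 7 | L = 14 |
|---|---|---|
| 3 | 10% | 1% |
| 7 | 37% | 14% |
| 10 | 50% | 25% |

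The residual depends heavily on an interval that the protocol does not give, so no single L can be justified from it. With L = 7 the example windows become days −28 to −8 and −91 to −50. Their lengths are still 21 and 42 days, so the null share stays 1/3, and the 365-day enrollment requirement covers the longer look-back.

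**The case against.** The strongest reply is that much of the design is still open. The exposure assessment window, the incident-exposure rules, the choice of fixed or varying window and the scan statistic all go to the SAP, and days −21 to −1 are only an example. Nothing prevents the SAP from adding a lag. That stands, and the point does not rest on a missing SAP detail. It rests on what the protocol does fix: onset equals the first code, same-day exclusion is the only stated safeguard, and the limitations section does not name the bias.

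The analysis is also labelled exploratory. Section 9.1.7.3.2 warns of false alarms, requires separate controlled studies before any causal reading, and lets signals be set aside for obvious temporal confounding. That also stands, and it limits the harm to misdirected triage, not a wrong safety conclusion. But the section gives no criterion for what is obvious, and the claims-profile review is optional.

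The contrast with the SCRI is limited. Chart onset dates are used only when records are retrieved, and no chart review is planned for the scan's cases. The contrast shows that the protocol recognises the issue; it does not show that the scan could use onset dates directly.

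A reader might infer more than the text supports:
- **That false signals are certain.** With no onset-to-code interval and with triage available, the text supports only that they can arise.
- **That any early diagnosis can signal.** Apart from vaccines, only drugs and infections are in the tree, so symptom codes such as weakness cannot.
- **That weaker true signals would be masked.** This would need a conditional statistic, and that choice is left open.
- **That the lagged scan should be primary for some branches, and signals seen only without a lag classed as symptom-driven.** Separate primaries would split the single tree and its joint multiplicity adjustment, and automatic labelling could discard genuine short-latency infections.

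**Conclusion.** The point holds as a moderate design weakness with a cheap remedy. Drugs and infection diagnoses recorded between first symptoms and first G61.0 code can be counted as antecedent exposures, and neither self-control nor the day-0 rule removes them.

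The size is not derivable from the protocol. Under the stated assumptions about 1% of cases could be enough: 0.73% to 1.40% at 0.05/1000, with apparent rate ratios of 2.1 to 3.85. The conclusion depends on there being some gap between symptoms and first code, and on at least a small share of patients receiving a scanned drug or infection code within it. If either is negligible, so is the bias.

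**What to change.** - **Sections 9.1.1.3 and 9.1.7.3.1:** keep the planned scan and prespecify a lagged sensitivity scan. It excludes exposures in days −L to −1 and shifts the risk and comparison windows back by L. Applying the lag to the whole tree keeps the multiplicity adjustment intact.
- **Choice of L:** use several values, informed by the symptom-onset dates that Section 9.1.3.2 already has the Research Question 1 chart review record. That sample is stratified and comes from integrated delivery systems, while the scan uses national plans. The dates are therefore a guide, which is another reason for more than one value.
- **Section 9.1.9.3:** name exposure prompted by early GBS symptoms as a limitation.
- **Section 9.1.7.3.2:** flag a drug or infection signal that disappears under the lag as possibly prompted by early symptoms, without automatically dismissing it. This gives the triage step an objective basis.

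The cost is protocol and SAP wording plus additional TreeScan runs. The chart-review onset dates must be available before the lags are chosen; both parts belong to Research Question 1, whose final report is due 30 September 2026. True short-latency exposures will weaken in the lagged scan, which is why the unlagged scan is retained.

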# 9.1.2.1. Setting for GBS epidemiology and incidence

The source population for the GBS epidemiology and incidence objectives will be members from up to 3 national health plans; members from 1 or more regional integrated delivery systems or other data sources may also be included. The participation of specific RPs will be noted in the final SAP.

Individuals must meet all of the following inclusion criteria to be eligible for inclusion in this analysis:

- Research eligible at the participating RP;
- ≥18 years of age during the study period, January 2017 December 2024;
- Have ≥365 days of medical and pharmacy coverage preceding cohort entry, with gaps of ≤45 days permitted (they are considered administrative gaps, not lapses in health plan coverage); and
- Meet the algorithm for incident GBS (outlined in Table 1).
- There are no exclusion criteria for this analysis.

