#### Setting (Research Question 1)

- GBS epidemiology and incidence The source population will be members of multiple large national health plans; members from 1 or more regional integrated delivery systems or other data sources may also be included. Individuals will meet eligibility criteria if they are ≥18 years of age with ≥365 days of medical and pharmacy coverage preceding cohort entry between 2017 and 2024.
- GBS etiology: Medical record review The source population will be health plan members from regional integrated delivery systems with linked electronic health records (EHR) and administrative billing data. Individuals will meet eligibility criteria if they are ≥18 years of age with ≥365 days of medical and pharmacy coverage preceding cohort entry. Inpatient GBS diagnoses in the primary position will be identified via billed ICD-10-CM diagnosis codes in 2017 through 2024. Medical record review will be primarily conducted via direct access to the EHR, but charts may be requested as needed. To ensure the subgroups of interest (e.g., adults 18-59 years of age at increased risk of RSV-LRTD; adults with recent vaccination) are included in the medical record review, stratified random sampling of eligible cases identified in the billing data will be conducted, though oversampling of more recent GBS diagnoses may be needed.
- GBS etiology: Exploratory data mining-based signal detection The source population will be health plan members. Individuals will meet eligibility criteria if they are ≥18 years of age with ≥365 days of medical and pharmacy coverage preceding date of the incident GBS diagnosis between 2017 and 2024.

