# GBS epidemiology and incidence

#### Objectives:

- Estimate the incidence of GBS overall and in subgroups of interest (e.g., age, sex, comorbidities, region) over time.
- Describe individuals with GBS with respect to demographics, clinical characteristics, risk factors, treatment, and outcomes.
- GBS etiology
- Objectives:
- Conduct a detailed medical record review of a sample of GBS cases to validate a claims-based algorithm and to identify potential causes of GBS.
- Perform an exploratory data mining-based signal detection analysis to identify specific vaccines, drugs, and infections potentially associated with GBS.

#### 9.1.1. Study Design for Research Question 1

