# 9.1.4.3. Data Sources for GBS etiology: Exploratory data mining-based signal detection

The GBS etiology data mining-based signal detection objective will be conducted using health plan administrative claims data held by up to 3 national health plans (e.g., Carelon, Humana, and CVS Health). These RPs participate in the US FDA's Sentinel System. In addition to providing claims data in the SCDM, the RPs will provide scientific input and feedback to support this study.

#### 9.1.5. Study Size for Research Question 1

Data on all individuals meeting the applicable eligibility criteria within the contributing RPs will be analyzed for the GBS epidemiology and incidence objectives, and the data mining-based signal detection objective.

For the first 2 objectives, where we will estimate the incidence of GBS and describe individuals with GBS, the national health plans expected to participate in these analyses have provided preliminary counts of inpatient, incident GBS:  $\geq 1,000$  GBS cases among those 18-59 years of age and  $\geq 2,000$  among those 60 and older.

The medical record review objective will be conducted on approximately 300 cases.

#### 9.1.6. Data Management for Research Question 1

Please see Section 9.2.6 for Data Management details for the full study.

#### 9.1.7. Data Analysis for Research Question 1

Detailed methodology for summary and statistical analyses will be documented in the SAP, which will be dated, filed, and maintained by the sponsor. The SAP may modify the plans outlined in the protocol; any major modifications of primary endpoint definitions or their analyses would be reflected in a protocol amendment.

When appropriate, publicly available Sentinel analytic tools will be used for analyses. Modifications to the tools, when used, may be needed to meet study objectives, in which case the SAS programming data quality assurance (QA) standard operating procedures will be followed (see Figure 3). All statistical calculations will be performed using SAS 9.4 or higher.

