# 9.1.7.1. Data Analysis for GBS epidemiology and incidence

Descriptive statistics of adults 18 and older with GBS in 2017 through 2024 will be reported via frequencies and percentages for discrete variables and, for continuous variables, either means and standard deviations or medians and interquartile ranges. The incidence rate of GBS, and corresponding 95% CIs, will be estimated overall and for several subgroups, as described in Section 9.1.1.1, showing how and to what degree incidence rates vary across groups and whether there have been changes in rates during the study period.

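### Section 9.1.2.1 makes being a GBS case an entry criterion for the incidence analysis, contradicting the abstract and leaving the planned rates without a valid denominator

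*Protocol*

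**What the plan says.** Section 9.1.2.1 opens with the source population for both the incidence and the descriptive objective: members of up to three national health plans, possibly with others. It then states: "Individuals must meet all of the following inclusion criteria to be eligible for inclusion in this analysis". The list has four items: research eligibility, age 18 or over in the study period, at least 365 days of coverage before cohort entry, and "Meet the algorithm for incident GBS (outlined in Table 1"). It closes with "There are no exclusion criteria for this analysis". No second cohort is defined.

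Section 9.1.5 ties the analysis set to that list: "Data on all individuals meeting the applicable eligibility criteria within the contributing RPs will be analyzed for the GBS epidemiology and incidence objectives".

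The first objective is "Estimate the incidence of GBS overall and in subgroups of interest (e.g., age, sex, comorbidities, region) over time". Section 9.1.7.1 accordingly plans that "The incidence rate of GBS, and corresponding 95% CIs, will be estimated overall and for several subgroups", and Section 9.1.1.1 adds annual rates, including for people with certain infections, vaccinations or underlying conditions.

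The abstract, under Setting (Research Question 1), requires for the same objective only that people be "≥18 years of age with ≥365 days of medical and pharmacy coverage preceding cohort entry between 2017 and 2024". It does not mention GBS.

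**The concern.** An incidence rate divides new cases by the time at risk of everyone who could have become a case. An entry rule that only cases can satisfy suits the description of GBS patients, but it removes all time contributed by members who never developed GBS. One list governs both objectives, so the rate inherits a rule that fits only the description.

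Incidence by year and subgroup is the first objective of Research Question 1, and Section 7 gives the lack of published subgroup rates as part of the rationale. Section 9.2.5.2 also says the number of vaccinees needed for the SCRI study may be revised in the light of this incidence. Programs are written centrally and run by the partners (Section 9.2.6), so the criteria need to say what is meant.

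**Working it through.** The protocol states no Research Question 1 rate, person-time or precision, so there is no planned figure to reproduce. The check sets the texts side by side and then shows what the literal rule would return.

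**Side by side**

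| Objective | Abstract, Setting | Body |
|---|---|---|
| Epidemiology and incidence | Age and coverage only | 9.1.2.1: age, coverage **and** GBS algorithm met |
| Medical record review | Age and coverage, then primary inpatient GBS diagnoses identified | 9.1.2.2: essentially the same four criteria |
| Data mining | Age, and coverage counted back from the GBS diagnosis | 9.1.2.3: essentially the same four criteria |

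The abstract separates the incidence objective from the two case-only objectives; the body does not. The GBS criterion fits 9.1.2.2 and 9.1.2.3, where only cases are studied. In 9.1.2.1 it conflicts with the rates planned in 9.1.1.1 and 9.1.7.1.

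**What the literal rule returns**

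- Inputs: n cases; y years contributed per case, at most 8 (2017 through 2024, Section 9.1.7.1).
- Formula: rate = n / (n × y) = 1 / y. The number of cases cancels.
- y = 8: 1/8 = 12,500 per 100,000 person-years.
- y = 4: 1/4 = 25,000 per 100,000.
- y = 1: 1/1 = 100,000 per 100,000.
- Against the 2 per 100,000 assumed in Section 9.2.5, the lowest of these is 12,500 / 2 = 6,250 times too high.

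The result depends only on length of follow-up and carries no information on how common GBS is.

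**Scale of the missing denominator (illustration only)**

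- Inputs: at least 1,000 cases aged 18-59 (Section 9.1.5); 2 per 100,000 person-years (Section 9.2.5).
- 1,000 / 0.00002 = 50 million person-years.
- At half that rate, 1,000 / 0.00001 = 100 million; at double, 1,000 / 0.00004 = 25 million.

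The 2 per 100,000 is assumed for adults aged 18-59 at increased risk of RSV-LRTD, whereas the 1,000 cases are all those aged 18-59. The figure therefore shows an order of magnitude and is not an estimate.

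**Subgroups**

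Table 2 describes cases and counts its windows back from the GBS diagnosis. A member without GBS has no such date. A rate by recent infection or vaccination therefore needs the corresponding person-time among all eligible members, which a case-only cohort cannot provide.

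**The case against.** The intent can be read from the protocol. Section 9.1.2.1 itself names health plan members as the source population, the abstract omits the GBS requirement, and Section 9.1.1.1 first plans rates and then describes the people found to have GBS, a step that would be redundant if everyone analysed had it. Detailed methods go to the SAP, and Section 9.2.8 has programming specifications reviewed and approved, so someone would probably notice a rate without a denominator.

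Most of this stands. It shows that the fault is a contradiction, probably text shared with the two case-only sections, and not a decision to study incidence in cases. It does not repair the eligibility text. The protocol does not leave the incidence population open for the SAP; it states one, and the stated one is wrong. Naming a source population is also not enough: cases must satisfy 365 days of coverage and a 365-day washout, and the denominator must meet the same conditions, yet the section applies coverage only to people who also meet the GBS algorithm.

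It is also fair that window lengths for infection and vaccination person-time belong in the SAP. Their absence here is no fault.

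**Conclusion.** The inconsistency is real and should be corrected. As written, Section 9.1.2.1 contradicts the abstract and the planned incidence rates, and followed literally it yields a quotient of at least 12,500 per 100,000 person-years that does not estimate incidence. This rests on taking the requirement to meet all criteria at its word and on Section 9.1.5, which analyses those who satisfy them.

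A reader might infer more, and the documents do not support it:

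- That the study is designed so that it cannot estimate incidence. The abstract and the order of steps in 9.1.1.1 point to a full-membership denominator.
- That there is no person-time at all. Cases have their own time before diagnosis; what is missing is the time of non-cases.
- That the safety tests are compromised. The historical comparator RCA computes its background rates in its own vaccinated comparator group (Sections 9.2.2.1.1.2 and 9.2.7.1.2), and the concurrent RCA and the SCRI compare windows among ABRYSVO vaccinees.
- That the SCRI size must change with this result. Section 9.2.5.2 only allows for a revision.

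**What to change.** In Section 9.1.2.1, replace the single list by two populations.

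1. **Incidence cohort:** all research-eligible members aged 18 or over with at least 365 days of coverage (gaps as already allowed) and no G61.0 or G65.0 code in the prior 365 days. GBS as defined in Table 1 is the outcome. Person-time ends at GBS, disenrollment, death or the end of the study period.
2. **Descriptive cohort:** the members of that cohort who meet the Table 1 algorithm. The GBS criterion applies here only.

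Add one sentence saying that, where incidence is reported by recent infection or vaccination, the denominator is the corresponding person-time among all eligible members, with windows set in the SAP. Bring the abstract's Setting text and Section 9.1.5 into line.

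The cost is one amended criteria list and matching wording in two places. Coverage and diagnosis codes are already part of the planned criteria, so no new kind of data should be needed, although the documents do not confirm this for every partner that might be added.
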